### **8.2.2 Immunology Assays**

Anti-Na-GST-1 IgG antibody, other humoral, innate immunity and cellular assays will be performed at the Department of MITM of the George Washington University School of Medicine and Health Sciences. All cryopreservation of plasma, sera and peripheral blood mononuclear cells (PBMCs) will be in liquid nitrogen.

#### **8.2.2.1 Anti-Na-GST-1 Antibody Assays**

Antibodies to Na-GST-1 will be measured in serum or plasma of study subjects using an indirect ELISA assay. Antigen-specific IgG and IgG1-4 antibody levels will be measured at baseline and at several time-points post-vaccination. For the indirect ELISA method, microwell plates will be adsorbed with purified recombinant Na-GST-1, blocked, and incubated with test sample sera or plasma, and then incubated overnight at approximately 4°C. Plates will then be washed and a horseradish peroxidase conjugated anti-human antibody (e.g., anti-human IgG) will be added and incubated with plates. Plates will be washed again, incubated with a chromogenic substrate, and then the Optical Density (OD) of the samples read using an automated ELISA plate reader. Levels of antibodies against Na-GST-1 in sera or plasma will be converted to Arbitrary Units of antibody by homologous interpolation of their OD readings from a standard reference curve derived from serial dilutions of a Standard Reference Serum unique to each antibody isotype.

Surface Plasmon Resonance (SPR) will be used to measure the affinity of antibody interactions with recombinant Na-GST-1 antigen. SPR determines the immunoreactivity and affinity of

antibody responses in numerous contexts as it measures rates of antibody-antigen association and dissociation based on the Law of Mass Action to assess antibody affinity.

#### **8.2.2.2 Enzyme Neutralization Assays**

An *in vitro* assay has been developed to measure the functional capacity of antibodies induced by vaccination with recombinant Na-GST-1 to inhibit or neutralize the catalytic activity of the native form of this protein. Serum or plasma samples collected from study subjects will be tested for their neutralizing capacity at several post-vaccination time points. These assays will be performed at the Clinical Immunology Laboratory of the Department of MITM of the George Washington University.

#### **8.2.2.3 Memory B Cell Measurement**

The ELISPOT method will be used to evaluate the induction of memory B cells (MBCs) after each vaccination and the maintenance of MBCs throughout the vaccination schedule to determine if MBCs act as surrogate markers (biomarkers) for later antibody production.

#### **8.2.2.4 Cellular and Innate Immunity Assays**

PBMCs will be isolated by Ficoll gradient and the circulating dendritic cell (DC) population isolated by affinity columns according to standard protocol. The DC population will be cultured *in vitro* and the cells will either remain “un-stimulated” or be “stimulated” with a TLR7/8 agonist (1 µg/ml, 4-amino-2-ethoxymethyl- $\alpha$ ,  $\alpha$ -dimethyl-1H-imidazoquinoline-1-ethanol). After 24 hours of stimulation, the supernatants will be collected and assayed for cytokine production (e.g., Interleukin (IL)-12, IFN-gamma, TNF-alpha, IL-4, IL-5 and IL-18) by commercially available ELISA kits. The pellet collected from the culture will be assayed for the cytokines by real-time (RT) PCR. In addition, purified DCs will be directly assayed for positive co-stimulatory molecules such as CD40, CD80, CD86 CD83, HLA-DR, PD-L1, and ICOSL by flow cytometry using commercially available labeled antibodies. The Natural Killer (NK) cell response generated in response to vaccination with Na-GST-1 administered with a TLR4 or TLR9 agonist will be compared to the response when Na-GST-1 is administered without these TLR agonists. At various points post-vaccination and post-CHHI, purified PBMCs will be stained with labeled anti-CD56 and the cells will be assayed for functionality by measuring cytokine production by intracellular staining. As functionality of NK cells can also be measured by their cytolytic activity, the cells will be analyzed for granzyme B and activation markers (e.g., NKG2D and NKP46) by flow cytometry. The cytotoxic activity of NK cells may also be assayed by using  $^{51}\text{Cr}$ -labeled K562 targets.

In addition, circulating DC and purified T cell populations will be separated by affinity columns. The DC will be cultured ( $1 \times 10^5$  cells/well) overnight and pulsed with the recombinant Na-GST antigen. The following day, purified T cells from the same individual will be added to the culture and after 48 hours of incubation the T cells will be evaluated for proliferation (Ki67 labeling), cytokine production (IL-2, IL-4, IL-5, IFN $\gamma$ , TNF $\alpha$ ), co-stimulatory molecules (CD40, CD40L, CD80, CD86, and ICOS), and inhibitory receptors (PD-1, PDL-1, LG-3, 2B4) by polychromatic flow cytometry.

### **8.2.3 Parasitology Assays**

#### **8.2.3.1 Fecal Egg Detection by Microscopy**

Fecal exams will begin with the super-saturated saline flotation technique to determine hookworm infection status (i.e., positive or negative). Fecal samples will be analyzed by the McMaster technique to determine the intensity of hookworm infection. To perform the McMaster examination, a fecal suspension is applied to a slide with counting chambers. Egg counts are performed under light microscopy.

#### **8.2.3.2 Adult Worm Counts**

During the 3-day albendazole treatment period at the end of the study, subjects will be asked to provide all fecal material passed, which will be examined for expelled worms. Worms will be washed in phosphate-buffered saline and stored in ethanol. The worms will be clarified in a phenol solution and the mouthparts examined under a microscope.

#### **8.2.3.3 Polymerase Chain Reaction (PCR) Test for *N. americanus***

A quantitative PCR assay will be used to detect and quantify *N. americanus* DNA in fecal samples collected from study participants. DNA will be isolated from a small sample of feces (~50 mg), and *Necator* DNA amplified by real-time quantitative PCR using primers and probe specific for the internal transcribed spacer 2 (ITS2) of *N. americanus* (73).

## **8.3 Specimen Preparation, Handling, and Shipping**

### **8.3.1 Instructions for Specimen Preparation, Handling, and Storage**

Instructions for specimen preparation, handling, and storage are included in the protocol-specific Manual of Procedures (MOP), as appropriate.

Blood specimens for clinical screening and safety labs will be tested locally by the LabCorp® clinical laboratory.

Urine dipstick tests and urine pregnancy tests will be performed in the research clinic laboratory at the GW MFA.

Fecal specimens obtained for parasitology testing will be processed as specified in the MOP and transported to the Department of MITM at GWU for processing and storage.

Blood specimens for isolation of serum, plasma, and PBMCs will be collected as specified in the study MOP and transported to the Department of MITM at GWU for processing and storage.

### **8.3.2 Specimen Shipment**

Specimen shipment (primarily fecal samples to Baylor College of Medicine, Houston, TX) will occur at intervals during the course of the study following all applicable International Air Transport Association (IATA) requirements and according to the specifics for storage temperature and documentation as detailed in protocol-specific SOPs, as appropriate.

## 9 ASSESSMENT OF SAFETY

### 9.1 Specification of Safety Parameters

Safety will be assessed by the frequency and severity of:

1. Study product (vaccine or CHHI)-related serious adverse events occurring from the time of the first study vaccination through approximately 10 months after the last study vaccination.
2. Study vaccine-related solicited Adverse Events – reactogenicity events occurring on the day of each study vaccination through 14 days after each study vaccination:
  - a) Injection site reactions including erythema (redness), induration (hardness)/swelling, pain, and tenderness.
  - b) Systemic reactions including fever, myalgia (body aches/muscular pain exclusive of the injection site), arthralgia (joint pain exclusive of the injection site), headache, nausea, and vomiting.
3. CHHI-related solicited adverse events – reactogenicity events occurring on the day of CHHI through study Day 280 (time of treatment with first dose of albendazole):
  - a) Application site reactions including pruritus, rash, induration (hardness)/swelling, pain, and tenderness.
  - b) Gastrointestinal reactions including abdominal pain, abdominal bloating, flatulence, nausea, vomiting, and diarrhea.
  - c) Respiratory reactions (possibly due to migration of larvae through the lungs) including cough and sore throat.
4. Clinical safety laboratory adverse events occurring throughout the study. Parameters to be evaluated include WBC, ANC, absolute eosinophil count, hemoglobin concentration, and platelet count; ALT; creatinine; rheumatoid factor; and, anti-ds DNA antibodies.
5. Unsolicited Adverse Events – non-serious adverse events occurring from the time of each study vaccination through approximately 28 days after each vaccination and from study Day 140 (day of CHHI) through Day 297.
6. New-onset chronic medical conditions occurring from the time of the first study vaccination through approximately 10 months after the last study vaccination.
7. Adverse Events of Special Interest occurring from the time of the first study vaccination through approximately 10 months after the last study vaccination.

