### **2.3.1.3 Risks of Experimental Infection with *N. americanus* Larval Inoculum**

Expected adverse effects of being inoculated with *N. americanus* infective larvae are local skin reactions at the site of application of the larvae and gastrointestinal symptoms upon maturation of the parasites into adult hookworms in the small intestine of the host. Reported skin reactions include localized maculopapular or papulovesicular rash that may be significant and prolonged (up to a month) when higher doses ( $\geq 50$ ) of larvae are applied. Occasional respiratory symptoms may be experienced during the migration of larvae through the lungs, including dry cough, shortness of breath, and wheeze. Reported gastrointestinal symptoms include abdominal bloating and pain, flatulence, diarrhea, nausea, and vomiting.

As with any investigational product, there is a theoretical possibility of risks of CHHI about which we have no present knowledge. Subjects will be informed of any such risks should further data become available during the course of this or other clinical studies. Risks associated with chronic hookworm infection include iron deficiency, iron-deficiency anemia (associated with fatigue and malaise) and chronic gastrointestinal symptoms including flatulence, abdominal bloating, abdominal pain, diarrhea, nausea, and vomiting. However, these usually only occur after several months or years of infection, which will not occur during this study.

Volunteers in this study who are experimentally infected with the *N. americanus* Larval Inoculum may develop patent infections and shed hookworm eggs in their feces. It is extremely unlikely that a bystander individual – for example, someone living in the same household as the study subject – could become infected with *N. americanus* due to exposure to these hookworm eggs that are shed, for several reasons. First, to become infectious to humans, hookworm eggs must hatch to release larvae into the environment. Hatching and development into infective larvae require a moist and warm environment (optimally between 23-33°C) and a certain period of time, generally estimated to be at least a week. Second, *N. americanus* larvae can infect humans only by coming into contact with skin; they are not infectious by oral ingestion.

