#### Safety

The following parameters will be evaluated for each formulation of Na-GST-1, in comparison to the saline placebo control:

1. Frequency of solicited injection site and systemic reactogenicity, graded by severity, on the day of each study vaccination through 14 days after each study vaccination.
2. Frequency of solicited adverse events, graded by severity, on the day of CHHI through study Day 280.
3. Frequency of study vaccine-related Serious Adverse Events from the time of the first study vaccination through approximately 10 months after the last study vaccination.
4. Frequency of clinical safety laboratory adverse events.
5. Frequency of unsolicited adverse events, graded by severity, from the time of each study vaccination through approximately 1 month after each study vaccination; and from the time of CHHI through treatment with albendazole (Day 297).
6. Frequency of new-onset chronic medical conditions through approximately 10 months after the third study vaccination.
7. Frequency of Adverse Events of Special Interest through approximately 10 months after the third study vaccination.

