### Study Day 0 (Visit #1: Day of First Vaccination)

1. Verify that Informed Consent was obtained.
2. Verify that all applicable eligibility criteria have been met.
3. Perform abbreviated history (including concomitant medications) and physical exam, focusing on any acute complaints.
4. Obtain blood for hematology, biochemistry, rheumatoid factor, anti-dsDNA, anti-Na-GST-1 antibody and cellular immunology assays.
5. For females, obtain a urine sample for pregnancy testing. Test must be negative to proceed; a positive test will exclude the volunteer from the trial.
6. Record vital signs (blood pressure, oral temperature, and heart rate). Vital signs recorded pre-vaccination on Day 0 will be considered as baseline.
7. Subjects will be enrolled and randomly assigned to a study group by the vaccine manager prior to the first study vaccination.
8. Administer the vaccine in the deltoid muscle. Record the site of injection (i.e., right or left arm) on the appropriate data collection form.
9. Observe for at least 1 hour after vaccination to evaluate for immediate adverse reactions. During the 1-hour post-immunization wait period, study staff will discuss signs and symptoms of potential AEs, describe proper use of digital thermometers, injection-site reaction measurement tools, and subject symptom diaries.
10. Record vital signs at the end of the 1-hour post-immunization wait period.

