### 9.2.3 CHHI Reactogenicity

All subjects will be observed for at least 60 minutes after application of the *N. americanus* larvae during CHHI to detect and treat any immediate AEs. Subjects will also complete study memory aids after CHHI beginning with the day of larval application and through Day 280 when they will be treated with albendazole to cure their infections. For the first 4 weeks after application of the *N. americanus* Larval Inoculum, the memory aids will be used to record pruritus, pain, tenderness, rash and swelling at the site of larval application, as well as cough and sore throat (to capture symptoms that may possibly be related to larval migration through the lungs). Starting on Day 175 (approximately 5 weeks after CHHI) of the study until the participant receives their first dose of albendazole, the memory aids will be used to record nausea, vomiting, diarrhea, abdominal pain, abdominal bloating and flatulence. Female participants of childbearing potential will additionally capture on the memory aids the form of contraception they are using. The memory aids will include a printed reminder of the potential risks associated with use of albendazole during pregnancy.

Subjects will also be asked to record any medications taken and any emergency room or healthcare provider visits (other than routine check-ups) through Day 297. The subject memory aid will be reviewed with the subject at subsequent clinic visits.

CHHI reactogenicity events are AEs that are known to occur with hookworm infection. The following Toxicity Grading Scales will be used to grade solicited local (larval application site) and systemic (subjective and quantitative) reactions:

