**Table 3: Assessment of Solicited or Expected Adverse Event Severity – CHHI Phase**

Adverse Event	Grade	Severity
Pain at site of larval application	1	Aware of pain but it does not interfere with daily activity and no pain medication is taken
	2	Aware of pain; there is interference with daily activity or it requires use of pain medication
	3	Aware of pain and it prevents daily activity
Tenderness at site of larval application	1	Area immediately surrounding application site hurts only when touched or with arm motion, and it does not interfere with daily activity
	2	Area immediately surrounding application site hurts when touched or with arm motion, and it interferes with daily activity
	3	Area immediately surrounding application site hurts when touched or with arm motion, and it prevents daily activity
Rash at site of larval application	1	25 mm – 50 mm and does not interfere with daily activity
	2	51 mm – 100 mm or interferes with daily activity
	3	> 100 mm or prevents daily activity
Induration/swelling at site of larval application	1	25 mm – 50 mm and does not interfere with daily activity
	2	51 mm – 100 mm or interferes with daily activity
	3	> 100 mm or prevents daily activity
Pruritus at site of larval application	1	Easily tolerated, does not interfere with daily activity
	2	Interferes with daily activity
	3	Prevents daily activity
Abdominal pain	1	Easily tolerated, does not interfere with daily activity
	2	Interferes with daily activity
	3	Prevents daily activity
Abdominal bloating	1	Easily tolerated, does not interfere with activity
	2	Interferes with daily activity
	3	Prevents daily activity
Nausea	1	Easily tolerated, does not interfere with daily activity
	2	Interferes with daily activity
	3	Prevents daily activity
Vomiting	1	1-2 episodes in 24 hours and does not interfere with activity
	2	> 2 episodes in 24 hours or interferes with daily activity
	3	Prevents daily activity or requires outpatient IV hydration
Diarrhea	1	2-3 loose stools/24 hours
	2	4-5 stools/24 hours
	3	> 6 loose stools or requires outpatient IV hydration
Flatulence	1	Easily tolerated, does not interfere with daily activity
	2	Interferes with daily activity
	3	Prevents daily activity
Cough	1	Easily tolerated, does not interfere with daily activity
	2	Interferes with daily activity
	3	Prevents daily activity
Sore throat	1	Easily tolerated, does not interfere with daily activity
	2	Interferes with daily activity

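### The post-challenge diary asks about cough and sore throat but not shortness of breath or wheeze, two of the three lung-migration symptoms that the protocol names, so these are left to unsolicited reporting.

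*Protocol*

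**What the plan says.** Protocol Section 2.3.1.3, on the risks of the larval inoculum, states: "Occasional respiratory symptoms may be experienced during the migration of larvae through the lungs, including dry cough, shortness of breath, and wheeze".

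Section 9.1 item 3(c) lists the solicited respiratory events after challenge as "Respiratory reactions (possibly due to migration of larvae through the lungs) including cough and sore throat". Section 9.2.3 says that for the first four weeks the memory aid records application-site reactions "as well as cough and sore throat (to capture symptoms that may possibly be related to larval migration through the lungs". Table 3, which grades solicited post-challenge events, has respiratory rows for cough and sore throat only. SAP Section 5.7.5.3 repeats the memory-aid description with the same two items.

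Two primary safety outcomes in Protocol Section 3.2.1 matter here. Item 2 (item 3 in SAP Section 4.1) is "Frequency of solicited adverse events, graded by severity, on the day of CHHI through study Day 280". Item 5 (item 6 in the SAP) covers unsolicited events, including those from challenge through Day 297. Unsolicited events after challenge are graded with Table 2, which has rows for dyspnea and for acute bronchospasm. SAP Section 5.7.5.3 tabulates both solicited and unsolicited post-challenge events by severity and group.

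**The concern.** The respiratory diary items have a stated purpose, which is to pick up symptoms of larvae passing through the lungs. Measured against the protocol's own list of those symptoms, the diary misses two and includes one that is not on the list. A symptom on a diary is asked about each time the diary is filled in. A symptom off the diary is recorded only if the subject volunteers it or a clinician draws it out.

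The completeness of the challenge-safety description is at stake. A reader of the solicited post-challenge table would see a rate for sore throat and no line for breathlessness or wheeze. The respiratory symptoms could not be compared with each other, because some were prompted and others were not. Section 8.1 promises special attention to respiratory disorders possibly related to challenge, and Section 9.3.4 makes pneumonitis an event of special interest after challenge. Leaving two named lung symptoms unprompted fits poorly with both.

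**Working it through.** The plan states no figure to reproduce, and no sample size, alpha or rate enters the point. The check compares the lists and then the schedule.

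**Symptom lists**

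| Symptom | Named in Protocol 2.3.1.3 | Solicited (9.1 item 3(c), 9.2.3, Table 3, SAP 5.7.5.3) | Row in Table 2 (unsolicited) |
|---|---|---|---|
| Cough | yes (dry cough) | yes | yes |
| Shortness of breath | yes | no | yes (dyspnea) |
| Wheeze | yes | no | none of its own; nearest is acute bronchospasm |
| Sore throat | no | yes | no |

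Of the three named symptoms, one is solicited and 3 − 1 = 2 are not. Of the two solicited items, one is not named in the risk section. The word *including* in Section 9.1 could be read as leaving the list open, but the memory aid and Table 3 close it.

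**Where the two symptoms can be recorded.** They cannot enter primary safety outcome 2, which counts solicited events. They can enter primary safety outcome 5.

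**What is scheduled while the respiratory diary runs.** Larvae are applied on Day 140, and four weeks of diary run to Day 140 + 28 = Day 168. Section 7.3 and Appendix A schedule a telephone call on Day 143, clinic visits on Days 147 and 154, and then nothing until Day 175, a gap of 175 − 154 = 21 days. Two weekly memory aids are handed out on Day 154, covering 14 days, to Day 168. So for 14 of the 28 days, half of the respiratory window, the diary is the only scheduled instrument, and it does not mention either symptom.

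**Whether an objective measure fills the gap.** None is scheduled. Table 4 grades respiratory rate, but the vital signs specified for Day 140 are blood pressure, temperature and heart rate, and SAP Section 5.7.5 names the same three. The bronchospasm row of Table 2 depends on FEV1 and bronchodilator response, and Appendix A lists no spirometry.

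**Size.** The documents give no incidence for either symptom and no capture fraction for diary or unsolicited reporting. A calculated under-count would only return whatever values were assumed.

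**The case against.** The strongest reply is that nothing is lost. Unsolicited events are themselves a primary safety outcome, Table 2 grades dyspnea and bronchospasm, and the SAP tabulates them. Staff ask about acute signs and symptoms on Day 143, and take a history and examine the subject on Days 147 and 154. Subjects also note medications and any emergency or healthcare visit through Day 297, and medically attended events are flagged. Severe respiratory events would probably surface, and related events of special interest and Grade 3 hypersensitivity reactions feed the halting rules in Section 9.5. This stands, and it confines the likely shortfall to mild and moderate events.

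A second reply is that a risk disclosure is not a data-collection list. Section 2.3.1.2 names limited limb movement, lymphadenopathy, pruritus and malaise after vaccination, and Section 9.1 item 2 solicits none of them. This is fair as a general rule. It is weaker here because Section 9.2.3 gives the purpose of the respiratory items, and they do not match the symptoms that the protocol attributes to that cause.

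A third reply is prior experience. Section 2.1.9 reports over 100 challenged adults and Section 2.1.9.1 reports 20 at this site. Both describe skin and gastrointestinal effects and mention no respiratory event. That makes a large effect unlikely, although these summaries give only the most common events.

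A reader might also infer that enrolment leaves all but severe asthma unscreened. The documents do not support that. Besides criterion 18, criterion 4 excludes clinically significant pulmonary disease and criterion 22 excludes high-dose inhaled corticosteroids.

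**Conclusion.** The mismatch is real, and the SAP carries it forward. Shortness of breath and wheeze are left to unsolicited reporting. They stay within primary safety outcome 5 but cannot enter outcome 2, and mild or moderate events are likely to be captured less completely than sore throat. That likelihood rests on the ordinary assumption that prompted symptoms are reported more fully than unprompted ones. The documents neither demonstrate it nor allow its size to be calculated.

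Two stronger readings should be resisted. A reader might infer that challenge safety as a whole under-counts its main respiratory risk. The risk section calls these symptoms occasional, does not rank them, and puts dry cough, which is solicited, first. It also does not single out breathlessness or wheeze as signals of pneumonitis. A reader might also infer a biased comparison between vaccine and placebo. All four groups are challenged under blinding and use the same diary, and nothing in the documents points to differential capture.

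This is a cheap improvement to the completeness and comparability of the safety data and does not threaten the trial's conclusions.

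**What to change.** Reconcile Protocol Sections 2.3.1.3, 9.1 item 3(c), 9.2.3 and Table 3 with SAP Section 5.7.5.3. Add shortness of breath and wheeze to the solicited respiratory list, to Table 3, to the memory aid for the first four weeks, and to the solicited post-challenge tables. Grade both by interference with daily activity, as Table 3 already does for cough. Table 2's bronchospasm row is unsuitable for a diary, because a subject cannot self-grade FEV1 and no spirometry is scheduled.

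For subjects whose diaries are already complete, tabulate unsolicited dyspnea, wheeze and bronchospasm beside the solicited respiratory events and mark them as unprompted. If the diary changes part-way through the trial, report prompted and unprompted subjects with separate denominators.

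The cost is two more diary and case report form lines for four weeks, a slightly longer diary for subjects, and a protocol amendment to the IRB under Section 15.6.
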